6.1.1 Sample Size Evaluation on Primary Endpoints

VenousTSQ

Subject experience and satisfaction will be measured through a validated, patient-centered venous treatment satisfaction questionnaire (VenousTSQ). The VenousTSQ is designed to have two components, the VenousTSQe and the VenousTSQs. As a result of the different content of both components of the VenousTSQ, the related endpoints are split into two separate primary endpoints, being:

1. *Peri-procedural patient satisfaction* as measured by a validated, patient-centered venous treatment satisfaction questionnaire (VenousTSQe) at 30 days post index procedure;
2. *Overall patient satisfaction* as measured by a validated, patient-centered venous treatment satisfaction questionnaire (VenousTSQs) at 30 days post index procedure.

While the VenousTSQ is a newly developed Patient Reported Outcome Measure (PROM), the questionnaire provides sufficient insight in the eventual scoring scales. Each of the two parts consists of

8-11 items in total. VenousTSQe consists of 8 items with items being able to be scored from 0 - 6. VenousTSQs consists of 11 items and items can similarly be scored from 0 - 6. Consequently, VenousTSQe and Venous TSQs have a potential scale that range runs from 0 - 48 and 0 – 66, respectively. Sample sizes are provided below for different scenarios with a varying number of potential items.

To determine the variance (SD), a comparison was made to other treatment satisfaction questionnaires (TSQs) that were developed by the same expert group. The Macular TSQ (MacTSQ) was designed as a measure of patient satisfaction with treatment for macular disease. The questionnaire consists of two subscales with each a maximum score of 36 (6 questions each) and a single scale with a maximum score of 72 (12 questions). The SD was reported as 3.56 for subscale 1, 5.04 for subscale 2, and 7.30 for the single scale. The Diabetes TSQ (DTSQ) was designed as a measure of patient satisfaction with treatment for diabetes. The questionnaire consists of a scale with a maximum score of 48 (8 questions) and a typical SD is around 5.0. To determine the SD for the two VenousTSQ endpoints, an overestimate was made in comparison with literature findings. The SD was selected to be equal to the number of included items in the score.

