The null hypothesis on the primary endpoints of VenousTSQe and VenousTSQs at 30 days is that the VenaSeal™ system arm will have same PROM scale as that of the control (ETA or surgical stripping) arm. The alternative hypothesis is that the VenaSeal™ system arm will have a different PROM scale from that of the control arm. Rejection of the null hypothesis in favor of the VenaSeal™ system will signify that the treatment satisfaction with the VenaSeal™ system is superior to the treatment with ETA or surgical stripping. A minimum difference of 0.5 points per item, as a total score, is utilized as the minimum meaningful difference between comparison groups.

Specifically, the null (H_0) and alternative (H_a) hypotheses are:

$$H_0: p_A = p_C$$

$$H_a: p_A \neq p_C$$

Where p_A and p_C are the true PROM scale for the VenaSeal™ system arm and ETA or surgical stripping arm, respectively. The parameter assumptions are:

- $p_A - p_C = 0.5 * [\text{number of items}]$
- Common standard deviation of $1 * [\text{number of items}]$ points
- T test with two sided $\alpha = 0.0167$
- 1:1 randomization
- 7% attrition rate for VenousTSQ at 30 days

With these assumptions, a total of 237 subjects (220 evaluable, 110 in each arm) will yield 90% power to reject the null hypothesis in favor of the alternative hypothesis of superiority on VenousTSQe and VenousTSQs at 30 days in each study.

If a somewhat less conservative assumption is made for the standard deviation ($0.75 * [\text{number of items}]$), then there will still be reasonable power for the VenaSeal vs. Surgical Stripping study.

A 5 PROM point difference with a SD of 10 PROM points is assumed for 10 questions in either component of the VenousTSQ. Assuming the standard deviation increases with the number of questions and the minimum clinical difference of 0.5 points per question, the sample size calculations are not impacted by

the number of questions. Therefore, the sample size will not need to be adjusted based upon the number of items included in the score.

Number of Venous TSQ questions	Difference of PROM Points	SD of PROM points (assuming equal in both arms)	Sample size (1:1 evaluable)
6	3	6	110:110
8	4	8	110:110
10	5	10	110:110
12	6	12	110:110

Elimination of truncal reflux

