The third primary endpoint is the elimination of clinically relevant superficial truncal disease in target veins at the index procedure. This endpoint will be measured as a percentage of treated vein vs. diseased vein for each target vein.

Based on clinical experience, the minimal clinically relevant difference in mean percentage of truncal disease elimination between treatment modalities is expected to be 10%. To calculate the sample size, a combination of the smallest minimal clinically relevant difference and the largest variance (SD) are justified being the conservative assumptions. A SD of 20% is used to calculate the sample sizes.

The null hypothesis on this primary endpoint is that the VenaSeal™ system arm will have the same percentage of reflux eliminated at the index procedure as that of the control (ETA or surgical stripping) arm. The alternative hypothesis is that the VenaSeal™ system arm will have the different percentage of reflux eliminated at the index procedure from the control arm. Rejection of the null hypothesis in favor of the VenaSeal™ system will signify that the treatment with the VenaSeal™ system is superior to the treatment with ETA or surgical stripping if the percentage of reflux treated for the VenaSeal™ system is greater than control.

Specifically, the null (H_0) and alternative (H_a) hypotheses are:

$$H_0: \mu_A = \mu_C$$

$$H_a: \mu_A \neq \mu_C$$

Where μ_A and μ_C are the percentage of reflux treated at the index procedure for the VenaSeal™ system arm and ETA or surgical stripping arm.

The parameter assumptions are:

- $\mu_A - \mu_C = 10\%$
- Common standard deviation of 20%
- Two-sided t test with $\alpha = 0.0167$
- 1:1 randomization
- 3% attrition

With these assumptions, a total of 227 subjects (220 evaluable, 110 in each arm) will yield 90% power to reject the null hypothesis in favor of the alternative hypothesis of superiority in each study.

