7.5 Adjustments for Multiple Comparisons

In the randomized studies, Hochberg procedure will be used in the adjustments for multiple comparisons on primary and key secondary endpoints (Benjamini & Hochberg, 1995)¹. Familywise type I error 0.05 will be used for the primary endpoints and type I error preserved from the primary endpoints will be used for the key secondary endpoints.

VenaSeal vs. ETA Randomized Study

In each randomized study, p-values for the primary endpoints will be ordered from largest to smallest as $p_{p1} > p_{p2} > p_{p3}$ from the 3 hypothesis tests H_{p1}, H_{p2} and H_{p3} , and for the key secondary objectives in descending order as $p_{s1} > p_{s2}$ from the 2 hypothesis tests for key secondary endpoints H_{s1} and H_{s2} , the procedure is as follows:

Step 1. If $p_{p1} < \alpha$, then claim success on all 3 hypotheses for primary endpoints H_{p1}, H_{p2} and H_{p3} ; and proceed to Step 1a, otherwise, go to step 2.	
Step 1a. If $p_{s1} < \alpha$, then claim success on both hypotheses for key secondary endpoints H_{s1} and H_{s2}; otherwise, go to step 1b.
 
Step 1b. If $p_{s2} < \alpha/2$, then claim success on hypothesis for key secondary endpoint H_{s2}; otherwise, both hypotheses for key secondary endpoints H_{s1} and H_{s2} are unsuccessful

Step 2. If $p_{p2} < \alpha/2$, then claim success on two hypotheses for primary endpoints H_{p2} and H_{p3} ; and proceed to Step 2a, otherwise, go to step 3.	
Step 2a. If $p_{s1} < \alpha/2$, then claim success on both hypotheses for key secondary endpoints H_{s1} and H_{s2}; otherwise, go to step 2b.
 
Step 2b. If $p_{s2} < \alpha/4$, then claim success on hypothesis for key secondary endpoint H_{s2}; otherwise, both hypotheses for key secondary endpoints H_{s1} and H_{s2} are unsuccessful

Step 3. If $p_{p3} < \alpha/3$, then claim success on hypothesis for primary endpoint H_{p3} ; and proceed to Step 3a, otherwise, no success on all 3 hypotheses for primary endpoints H_{p1}, H_{p2} and H_{p3}	
Step 3a. If $p_{s1} < \alpha/3$, then claim success on both hypotheses for key secondary endpoints H_{s1} and H_{s2}; otherwise, go to step 3b.
 
Step 3b. If $p_{s2} < \alpha/6$, then claim success on hypothesis for key secondary endpoint H_{s2}; otherwise, both hypotheses for key secondary endpoints H_{s1} and H_{s2} are unsuccessful

$\alpha = 0.05$ for Endothermal Ablation (ETA) study.	

VenaSeal vs. Surgical Stripping Randomized Study

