In each randomized study, p-values for the primary endpoints will be ordered from largest to smallest as $p_{p1} > p_{p2}$ from the 2 hypothesis tests H_{p1} , and H_{p2} , and for the key secondary objectives in descending order as $p_{s1} > p_{s2}$ from the 2 hypothesis tests for key secondary endpoints H_{s1} and H_{s2} , the procedure is as follows:

Step 1. If $p_{p1} < \alpha$, then claim success on both hypotheses for primary endpoints H_{p1} , and H_{p2} ; and proceed to Step 1a, otherwise, go to step 2.	
Step 1a. If $p_{s1} < \alpha$, then claim success on both hypotheses for key secondary endpoints H_{s1} and H_{s2}; otherwise, go to step 1b.
 
Step 1b. If $p_{s2} < \alpha/2$, then claim success on hypothesis for key secondary endpoint H_{s2}; otherwise, both hypotheses for key secondary endpoints H_{s1} and H_{s2} are unsuccessful

Step 2. If $p_{p2} < \alpha/2$, then claim success on endpoint H_{p2} , otherwise, no success	
Step 2a. If $p_{s1} < \alpha/2$, then claim success on both hypotheses for key secondary endpoints H_{s1} and H_{s2}; otherwise, go to step 2b.

on both hypotheses for primary endpoints H_{p1} , and H_{p2}	Step 2b. If $p_{s2} < \alpha/4$, then claim success on hypothesis for key secondary endpoint H_{s2} ; otherwise, both hypotheses for key secondary endpoints H_{s1} and H_{s2} are unsuccessful
$\alpha = 0.05$ for VenaSeal vs. Surgical Stripping Randomized Study.	

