7.9.1.1.3 Rationale for Performance Criteria

If the null hypothesis is rejected, it demonstrates that the treatment satisfaction or percentage of the target vein successfully treated with the VenaSeal™ system is significantly different from the treatment with ETA or surgical stripping.

When the two-sided P-value is less than the pre-specified critical value alpha per adjustment of multiple comparison (described in Section 7.5) and the mean of certain primary endpoint in treatment with VenaSeal™ is greater than that in control of ETA or Surgical Stripping, the superiority of treatment with VenaSeal™ on that primary endpoint can be declared.

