7.9.1.1.4 Analysis Methods

VenousTSQe and VenousTSQs consist of 8 and 11 items, respectively, with each item having the possibility to be scored from 0-6. The scores will be collected from eCRFs at 30 days.

The VenousTSQe score is calculated as:

Item 1 (from the VenousTSQs) + Item 2 + Item 4 + Item 5b + Item 6b + Item 7

Items 1, 3, and 8 from the VenousTSQe are not used.

Since the VenousTSQe score is the sum of 6 items, it can range from 0 to 36.

The Venous TSQs score is calculated as:

Item 1 + Item 2 + Item 4b + Item 6 + Item 7b + Item 9

Items 3, 5, 8, 10 and 11 are not used.

Since the VenousTSQs is the sum of 6 items, it can range from 0 to 36.

Scoring Notes

Some items included in the scores are skipped when they are not applicable, based on a previous question. For example, consider 5a and 5b in the VenousTSQe

5a asks: "Immediately after the procedure, did you wear compression stockings or bandages?" If the response to 5a is "no", 5b is skipped. 5b asks "How bothered were you by wearing compression stockings / bandages?", so it doesn't apply if no stockings / bandages were worn. In these cases, when an item in the score is skipped because of a response to the prior, related question, it will be scored as 6. For item 5b, 6 indicates "not bothered at all", which is sensible, since a person cannot be bothered by stockings that are not worn.

If the follow-up question is supposed to be skipped, but is not, the follow-up response will be used only if it is consistent with the prior, related question. If 5a is marked "no" (indicating that stockings were not worn), and 5b is not skipped, then:

- If 5b = 5 or 5b = 6, 5b will be used to calculate the score.
- If 5b < 5, then the responses are inconsistent, and 5b will be considered missing.

If a prior question is marked "yes", but the follow-up question is left blank, then the item will be considered missing:

- If 5a is marked "yes", but 5b is missing, then 5b will be considered missing.

Calculating the Score When Items are Missing

The VenousTSQe and VenousTSQs scores are missing when any of the included items is missing.

Hypothesis Test of the TSQ

(Shapiro-Wilk test) Normality on the outcomes of primary endpoints of PROM scores and % of target vein length successfully treated will be checked in each treatment arm first.

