If one of the treatment arms is not normal for a primary endpoint ($p < 0.05$), Wilcoxon rank-sum test will be used in the comparison between VenaSeal™ arm and control arm (ETA or Surgical Stripping). The test

statistic can be calculated by $Z = \frac{|R_1 - \mu_{R_1}| - 0.5}{\sigma_{R_1}}$ using normal approximation with 0.5 continuity correction, where R_1 is the summary of rank of PROM scores in treatment (VenaSeal) arm, μ_{R_1} is the expectation of R_1 and $\sigma_{R_1}^2$ is the variance of R_1 . Null hypothesis can be rejected if $|Z| > Z_{\alpha/2}$ and P value can be calculated by $1 - \Phi(Z)$.

If both treatment arms are normal for a primary endpoint, Two-sample T test will be used in the comparison between VenaSeal™ arm and control arm (ETA or Surgical Stripping). Null hypothesis can be rejected if the test statistic t has $|t| > t_{\frac{\alpha}{2}, N-1}$. If the Equality of Variances output has a p value ≥ 0.05 , the “pooled” variance will be computed as the weighted average of the sample variances; if the Equality of Variances output has a p value < 0.05 , the “Satterthwaite” will be computed as the weighted average of the sample variances.

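### SAP 7.9.1.1.4 prints a Wilcoxon p-value formula, 1 − Φ(Z), that is half the two-sided p-value and contradicts the rejection rule beside it

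*SAP*

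**What the plan says.** SAP 7.9.1.1.4 first runs a Shapiro-Wilk check in each arm ("Normality on the outcomes of primary endpoints of PROM scores", and on the percentage of vein length treated). If either arm fails at p < 0.05, that endpoint is compared by the Wilcoxon rank-sum test; otherwise a t test is used. The Wilcoxon statistic is Z = (|R1 − μ| − 0.5)/σ, where R1 is the rank sum in the VenaSeal arm and μ and σ² are its expectation and variance. The decision sentence is: "Null hypothesis can be rejected if $|Z| > Z_{\alpha/2}$ and P value can be calculated by $1 - \Phi(Z", completing as 1 − Φ(Z).

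The surrounding primary-endpoint text is two-sided:

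- SAP 7.9.1.1.1 sets not-equal alternatives.
- SAP 7.9.1.1.3 allows a superiority claim "When the two-sided P-value is less than the pre-specified critical value alpha per adjustment of multiple comparison", points to Section 7.5 for that value, and also requires the VenaSeal mean to be greater.
- SAP 6.1.1 sizes the questionnaire endpoints with "T test with two sided $\alpha = 0.0167" and vein length with "Two-sided t test with $\alpha = 0.0167".
- The t-test rule in 7.9.1.1.4 uses the α/2 critical value.

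SAP 7.5 then decides on p-values, not on Z. In its words, "p-values for the primary endpoints will be ordered from largest to smallest as" the list that follows, and these are compared with α, α/2 and, in the ETA study, α/3. For the Surgical Stripping study, if the larger p-value is below α, "then claim success on both hypotheses for primary endpoints". Section 7.5 does not itself say whether the primary p-values are one- or two-sided.

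**The concern.** The two halves of the decision sentence define different tests. The rejection rule is two-sided. The p-value is a single tail of a statistic whose sign has been removed, so it is not a directional one-sided p-value either: it takes the tail on whichever side happened to be observed.

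This matters because Section 7.5 consumes p-values, and this is the only p-value formula printed for a primary endpoint. A one-sided p-value would not look out of place there, since SAP 7.9.1.2.3 sends one to Section 7.5 for the closure endpoint. The choice of test is made endpoint by endpoint, so a halved Wilcoxon p-value could also be ranked against a correct two-sided t-test p-value. A false primary success would open the gate to the key secondary endpoints as well; that last effect has not been quantified.

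**Working it through.** **1. The design is two-sided.** SAP 6.1.1 assumes a difference of 0.5 per item, SD of 1 per item (standardised difference 0.5), two-sided α = 0.0167, 90% power and 7% attrition. The normal approximation gives 2 × (2.393 + 1.282)² / 0.5² ≈ 108.0, so 109 per arm. The noncentral t distribution gives power 0.8986 at 109 and 0.9016 at 110, which reproduces the stated 110 per arm. Attrition: 220 / 0.93 = 236.6, so 237, as stated. A one-sided 0.0167 would need only about 93 per arm.

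**2. The printed P against the two-sided p-value.** The two-sided value is 2 × [1 − Φ(Z)]; the printed one is 1 − Φ(Z).

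| Z | Printed P | Two-sided p |
|---|---|---|
| 1.80 | 0.0359 | 0.0719 |
| 1.90 | 0.0287 | 0.0574 |
| 1.96 | 0.0250 | 0.0500 |

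Requiring the printed P to be below α is the same as Z above the one-sided critical value: 1.645 instead of 1.960 at α = 0.05, and 2.128 instead of 2.394 at α/3. At α = 0.05 the two halves of the sentence disagree for every Z between 1.645 and 1.960.

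**3. The full formula on tied scores.** Null trials were simulated with scores rounded and clipped to 0–36, a tie-corrected variance and the 0.5 continuity correction: 3,000 trials per setting, 110 and 50 per arm, assumed means 18–31, SD 3.56, 5.04 and 6. The first two SDs are the 36-point subscale values quoted in SAP 6.1.1 ("The SD was reported as 3.56 for subscale 1, 5.04 for subscale 2"); the third is one point per item for six items. The printed P fell below 0.05 in 8.8–11.2% of trials and the two-sided p-value in 4.4–5.8%.

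**4. Family-wise error if the printed P enters Section 7.5.** Take the global null with independent endpoints, all on the Wilcoxon branch. Each printed P is below 0.05, 0.025 and 0.0167 with probability 0.10, 0.05 and 0.0333.

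- Surgical Stripping (two endpoints), any direction: 0.10² + 2 × 0.05 × 0.90 = 0.010 + 0.090 = 10.0%. With two-sided p: 0.05² + 2 × 0.025 × 0.95 = 5.0%.
- Surgical Stripping, false VenaSeal superiority: 0.010 × 0.75 + 0.090 × 0.5 = 5.25%. With two-sided p: 0.0025 × 0.75 + 0.0475 × 0.5 = 2.56%.
- ETA (three endpoints), any direction: 0.10³ + 3 × 0.90 × 0.05² + 3 × 0.0333 × (0.95² − 0.05²) = 0.0010 + 0.0068 + 0.0900 = 9.8%. With two-sided p: 0.0001 + 0.0018 + 0.0475 = 4.9%.

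Simulation (2,000,000 draws per scenario) extends this to assumed equal correlations between endpoints:

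| Study, any direction | Correlation 0 | 0.5 | 0.9 |
|---|---|---|---|
| ETA, printed P | 9.8% | 8.9% | 7.0% |
| ETA, two-sided p | 4.9% | 4.6% | 3.5% |
| Stripping, printed P | 10.0% | 9.5% | 8.3% |
| Stripping, two-sided p | 5.0% | 4.8% | 4.2% |

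Over correlations from 0 to 0.9, false VenaSeal superiority is 3.5–5.1% with the printed P against 1.7–2.5% (ETA), and 4.1–5.3% against 2.1–2.6% (Stripping).

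With fewer endpoints on the Wilcoxon branch the effect shrinks. For ETA, error in either direction is 4.7–6.6% with one endpoint on it and 5.8–8.2% with two. For Stripping it is 6.3–7.5% with one.

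**5. How often the branch is used.** The documents give no score distributions. In the simulated settings of step 3, Shapiro-Wilk rejected in at least one arm in anything from 10% to 100% of trials. At 110 per arm and SD 5.04, for example, it was 17% at a mean of 18 and 95% at a mean of 28. Scores near the ceiling almost always go to Wilcoxon. Vein length was not modelled.

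**The case against.** The strongest reply is that the SAP already settles the matter. Section 7.9.1.1.3 is the success criterion; it says the p-value is two-sided and names Section 7.5 as the place where it is used. The hypotheses, the design tests, the t-test rule and the first half of the sentence in question all agree with it. Harm requires someone to program the stray formula and pass its output to Section 7.5 against all of that. The SAP specifies SAS or other accepted software, and for the VCSS Wilcoxon comparison it shows procedure code, not a hand calculation. Even in the worst case, the requirement that the VenaSeal mean be greater holds false superiority near 5%, and with one ETA endpoint affected at high correlation the error can stay below 5%.

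Most of this stands, and it limits the weight of the point. The inflation is conditional, the t-test branch and the sample size are untouched, and the false-superiority figure is the more relevant one. It does not make the formula right. Level I validation of primary analyses is planned, but its content is not described, so it cannot be assumed to catch the error. A factor of 2 lost when the PDF was converted to text cannot be fully excluded, although the expression reads as complete.

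**Conclusion.** The concern holds. The printed p-value is half the two-sided p-value, exactly so under the normal approximation whenever the absolute rank-sum deviation is at least 0.5, and no other part of the SAP corrects it. The consequence depends on which text is programmed. Under 7.9.1.1.3 or the adjacent rejection rule, nothing is inflated. Under the printed formula, family-wise error roughly doubles when all primary endpoints go to the Wilcoxon branch. That worst case assumes the global null and equal endpoint correlations of 0 to 0.9; how often the branch applies is unknown. This should be fixed before analysis: a primary result with Z between 1.645 and 1.960 should not be a success or a failure according to which half of one sentence was coded.

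**What to change.** In SAP 7.9.1.1.4 replace 1 − Φ(Z) with min{1, 2 × [1 − Φ(Z)]}, or refer to the two-sided p-value from the SAS Wilcoxon procedure. The cap is needed because the continuity correction makes Z negative when the rank-sum deviation is below 0.5. In SAP 7.5 add one sentence stating that the primary-endpoint p-values entering the procedure are two-sided. It repeats 7.9.1.1.3, but places the statement where the decisions are made, next to a closure p-value that is one-sided. The cost is one formula, one sentence and matching code, with no added data or patients.

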7.9.1.1.5 Determination of Subjects' Data for Analysis

ITT population with available data will be used for the primary analysis on primary endpoints. For the sensitivity analyses, PP and AT populations will be used on primary endpoints.

7.9.1.1.6 Sensitivity and Missing Data Analysis

It is recommended to perform an additional scoring of the TSQe that does not include Item 5, i.e. the Compression stockings question.

To account for missing data in the primary endpoint evaluation, two forms of imputation will be performed. For patients that have no baseline information collected, they will be assigned the average value of the TSQ in the control arm. For patients with a baseline visit and baseline information collected, multiple imputation will be performed as a sensitivity analysis. Subjects who do not obtain their VenousTSQe at 30 days, VenousTSQs at 30 days or the percentage of target vein treated at procedure will have these measurements imputed using PROC MI in SAS. The covariates to be used in the imputation model are age, gender, race, diabetes, CEAP classification, Historical Superficial and Deep Venous Treatment, Family History of Chronic Venous Disease, VCSS at baseline, 7 days and 30 days, Length of clinically relevant superficial truncal disease in target vein and treatment arms. Ten imputed data sets will be generated using regression method (REG option in PROC MI). The overall PROM scores for VenousTSQe and VenousTSQs and % target vein treated success and their standard errors will be generated for each of ten imputed data sets. PROC MIANALYZE in SAS will be used to summarize the overall treatment difference, standard error, and two-sided 95% confidence interval.

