10.4. Randomization and Treatment Assignment (CEAP 2-5)

After a patient has signed the ICF, the CEAP assessment has been completed, and the eligibility criteria are verified, the patient will be enrolled via randomization. There are two Randomized Studies:

1. VenaSeal vs. ETA Study: subjects will be 1:1 randomized to VenaSeal™ system or ETA treatment.
2. VenaSeal vs. Surgical Stripping Study: subjects were randomized 1:1 to VenaSeal™ system or surgical stripping treatment. VenaSeal vs Surgical Stripping Study was closed to enrollment as of 22-Feb-2022.

Each site will be designated as participating in only one of the two Randomized Studies and cannot participate in both. Which study the site will enroll into is pre-determined by geographical region and device/treatment availability (i.e., regulatory approval and reimbursable status). Randomization will be accomplished using the Oracle Clinical system (or paper back-up if the system is down) prior to the collection of Baseline visit data and will be stratified by the site and by CEAP (2004) clinical category to ensure balanced arms. Site personnel will obtain the subject's randomization sequence on the Randomization CRF which will be generated from the database. Randomization schedules will be prepared for each site using a random permuted block design stratified by site and CEAP (2004) (grouping categories 2-3 vs. 4-5).

If a subject is inadvertently randomized twice or more, the first assigned treatment arm will be used for the intention-to-treat analysis, and investigators should treat subjects according to the first randomization. Knowledge of the development of randomization lists may lead to selection bias, therefore these details will be described in a separate document. If a subject is inadvertently treated with the wrong treatment modality, this will be recorded as a protocol deviation.

Randomization may be done during the screening visit as applicable or may be completed closer to the Baseline visit if there will be a significant delay between Screening and Baseline.

CEAP 6, active VLU subjects will not be randomized and will be treated with the VenaSeal™ system.

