6.1 Randomized Studies

Analyses will be performed on all patients who pass the point of enrollment (randomization), as according to the intention-to-treat (ITT) principle. Patients will be analyzed in the arm they are randomized to regardless of the treatment received.

There are three primary endpoints and two key secondary endpoints with formal hypothesis testing for the Randomized Studies. Multiplicity adjustment needs to be considered to control the overall type I error. Each randomized study will have a family-wise type I error rate of 0.05. Within each study, Hochberg procedure will be used to control the family-wise type I error rate to 0.05 for the primary endpoints (Benjamini & Hochberg, 1995)¹. Type I error preserved from the primary endpoints will be used for the key secondary endpoints.

A type I error of 0.0167 will be used in the following sample size calculations for this purpose.

In the two Randomized Studies, three primary endpoints will be assessed:

- 1) Peri-procedural patient satisfaction as measured by a validated patient-centered venous treatment satisfaction questionnaire (VenousTSQe) at 30 days;
- 2) Patient satisfaction as measured by a validated patient-centered venous treatment satisfaction questionnaire (VenousTSQs) at 30 days, and
- 3) elimination of clinically relevant superficial truncal disease in each target vein at index procedure. The two key secondary endpoints include achieving the anatomical closure of primary target superficial truncal veins at 6 months and the time to return to work post-index procedure.

For VenaSeal vs Surgical Stripping Study, 108 subjects randomized before 22-Feb- 2022 will be included in the analysis. These subjects will be followed for 12 months after index procedure. Since the enrollment was stopped for the VenaSeal vs. Surgical Stripping Study with up to 108 subjects, there is still reasonable power for the two TSQs and key secondary objectives. Therefore, the VenaSeal vs. Surgical Stripping Study will test two primary endpoints (Venous TSQe and TSQs at 30 days) and the key secondary endpoints. The elimination of truncal reflux at the index procedure will be summarized but not tested for hypothesis testing.

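### The TSQ missing-data analysis gives every subject without baseline data the control-arm mean as a fixed value, which shrinks the difference and misstates its standard error when the filled fractions differ by arm

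*SAP*

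**What the plan says.** SAP 7.9.1.1.5 sets the primary analysis: "ITT population with available data will be used for the primary analysis on primary endpoints". SAP 7.9.1.1.6 then describes two ways of filling in missing primary endpoint data.

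- Without baseline data: "For patients that have no baseline information collected, they will be assigned the average value of the TSQ in the control arm".
- With baseline data: "For patients with a baseline visit and baseline information collected, multiple imputation will be performed as a sensitivity analysis". This uses ten data sets, combined with PROC MIANALYZE into a difference, a standard error and a 95% confidence interval.

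The first rule does not depend on arm, and no variance adjustment is stated for it. Only the second is called a sensitivity analysis, so the status of the first is not explicit. SAP 7.4 gives the purpose of these analyses as judging what missing data could do to the primary results.

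ITT subjects can lack baseline data because randomization is done "prior to the collection of Baseline visit data" (Protocol 10.4). Protocol Table 5 has an outcome group for subjects who are randomized and then leave with no procedure attempted. They remain in the ITT set.

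**The concern.** A subject who receives one fixed number counts as a full observation but adds no spread and no uncertainty. This has two separate consequences. A VenaSeal subject placed at the control mean contributes a difference of zero, so the estimated effect shrinks. A control subject placed at the control mean adds apparent sample size without information, so the standard error comes out too small.

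Both studies are open-label (Protocol section 6). The same section mentions different anesthesia, aftercare and cost to the patient by treatment, so uneven withdrawal after randomization is plausible. At stake is whether this analysis can show that the TSQ results survive missing data. Its bias and its error bars would depend on how many such subjects fall in each arm.

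**Working it through.** **Inputs.** The final scores have 6 items each (SAP 7.9.1.1.4). SAP 6.1.1 states: "A minimum difference of 0.5 points per item, as a total score, is utilized as the minimum meaningful difference between comparison groups". That is 0.5 × 6 = 3 points. The same section sets the SD equal to the number of items, so 6 points. On alpha: "A type I error of 0.0167 will be used in the following sample size calculations for this purpose" (SAP 6.1), with a "T test with two sided" alpha at that level, 1:1 allocation and 7% attrition at 30 days (SAP 6.1.1). The studies have about 264 (ETA) and 108 (stripping) subjects.

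**The plan's own figure.** n per arm = 2 × (2.393 + 1.282)² × (6/3)² = 108.03, so 109. The noncentral t distribution gives power 0.9016 at 110 per arm, and 220/0.93 = 236.6, so 237. This agrees with "a total of 237 subjects (220 evaluable, 110 in each arm) will yield 90% power".

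**Effect of the rule.** Let n be the subjects per arm, and fA and fC the filled fractions in the VenaSeal and control arms. Assume values are missing completely at random.

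- Estimated difference = (1 − fA) × observed difference. It does not depend on fC.
- Reported variance under the null = (SD²/n) × [(1 − fA) + (1 − fC)].
- True variance under the null = (SD²/n) × [(1 − fA) + (1 − fA)²/(1 − fC)].
- Hence reported SE / true SE = √[(1 − fC)/(1 − fA)], which equals 1 only if fA = fC.
- Actual type I error = 2 × [1 − Φ(z × ratio)], with z = 2.393 for 0.0167 and 1.960 for 0.05.

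**ETA study, 132 per arm, true difference 3.** Assume as an upper bound that all 7% attrition lacks baseline data: 0.07 × 264 = 18.5, taken as 18. The lower end is an assumed 4 subjects. SEs and error rates are under the null.

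| Filled, VenaSeal / control | Difference | Reported SE | True SE | Ratio | Type I error at 0.0167 | at 0.05 |
|---|---|---|---|---|---|---|
| 9 / 9 | 2.80 | 0.713 | 0.713 | 1.000 | 0.017 | 0.050 |
| 18 / 0 | 2.59 | 0.713 | 0.663 | 1.076 | 0.010 | 0.035 |
| 0 / 18 | 3.00 | 0.713 | 0.767 | 0.929 | 0.026 | 0.069 |
| 4 / 0 | 2.91 | 0.733 | 0.722 | 1.016 | 0.015 | 0.047 |
| 0 / 4 | 3.00 | 0.733 | 0.744 | 0.985 | 0.018 | 0.054 |

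Example, 0 / 18: fC = 18/132 = 0.136 and the ratio is √0.864 = 0.929.

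Simulation with 30,000 trials per scenario and a pooled t test agrees. With 0 / 18, type I error is 0.026 at 0.0167 and 0.068 at 0.05. With 18 / 0, type I error is 0.0095 at 0.0167, and power is 0.906 against 0.933 for the available-case analysis. Coverage of the true difference by the 95% interval is about 0.93 in both one-sided cases. The available-case analysis itself gives a difference of 3.00 and type I error of 0.016 to 0.017 at 0.0167, whatever the split.

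**Stripping study, 54 per arm.** 0.07 × 108 = 7.6, taken as 8. By simulation, all VenaSeal gives a difference of 2.55 and power 0.433 against 0.519. All control gives type I error 0.028 at 0.0167 and 0.069 at 0.05.

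**The case against.** The strongest reply is that no success claim rests on this rule. Superiority is declared from the available-case ITT test through the multiplicity steps in SAP 7.5 and 7.9.1.1.3. That stands. A reader might infer from the 0.026 or 0.068 that the trial's own type I error is inflated, but the documents do not support this. Those are error rates of a supporting analysis, and the sample size does not change either.

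Second, moving untreated VenaSeal subjects to a control-like value can be a reasonable conservative assumption, and for an ITT comparison the shrinkage is not clearly bias. This partly stands. But the SAP does not present the rule as conservative, and filling control subjects works the other way.

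Third, drawing from the control distribution does not remove the shrinkage or fully repair the standard error. This also stands. Take 18 subjects in one arm and ten imputations.

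- Within-imputation variance: 2 × 36/132 = 0.545.
- Between-imputation variance: (18/132)² × (36/18 + 36/132) = 0.042.
- Rubin SE: √(0.545 + 1.1 × 0.042) = 0.769.
- True SE, all control: √(0.767² + 0.042/10) = 0.770, so the error is cured.
- True SE, all VenaSeal: √(0.663² + 0.042/10) = 0.666, so the Rubin SE is about 16% too large, and the difference is still 2.59.

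Fourth, subjects without baseline data are only part of the 7%, and one-sided splits are extremes. This stands as a limit on size.

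Two further inferences go beyond the text. One is that these subjects left because they had learned their arm. Protocol 10.4 gives only the order of events, and Table 5 also lists COVID-19 exclusion as a reason for no procedure. The other is that the constants harm a rank test through ties. SAP 7.9.1.1.6 asks for combined differences and standard errors, not a rank test.

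**Conclusion.** The point holds for the missing-data analysis only. Shrinkage depends solely on the VenaSeal fraction filled, so it occurs with an even split (2.80 instead of 3.00 at 9 per arm) and is absent if only control subjects are affected. The SE error needs unequal fractions and has a direction: conservative if mainly VenaSeal, anti-conservative if mainly control. Its size runs from negligible at about 4 affected subjects to moderate at the 18-subject upper bound.

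These figures assume a true difference of 3, an SD of 6, values missing completely at random and the stated counts. Neither document says how many subjects will lack baseline data or how they will split. The change is worth making because the rule can err in either direction and is cheap to replace.

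**What to change.** Delete the single-value rule. Put all randomized subjects in the same multiple imputation, with incomplete covariates imputed by fully conditional specification (the FCS statement in PROC MI). Use arm, site, CEAP group and any screening data; the first three are known for everyone at randomization. Combine with PROC MIANALYZE. With little information on these subjects, the result should be close to the available-case analysis if data are missing at random.

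If a control-like assumption is wanted, make it a separate sensitivity analysis labelled as conservative. Draw from the control distribution within the multiple imputation. State that it shrinks the difference on purpose and that its Rubin SE can be too large.

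Report the number of subjects without baseline data by arm. The cost is SAP wording and a small change to the code. No data collection, sample size or primary test changes.
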